### **Objective**

Evaluation of Zemedy, a cognitive behavioral therapy-based digital therapeutic application for the treatment of irritable bowel syndrome

[figure not shown]
### **Background**

Irritable bowel syndrome (IBS) is defined as having recurrent abdominal pain associated with defecation or a change of bowel habits.i It is a common syndrome affecting 11% (ranging 1.1% to 45%) in prevalence worldwide.ii The pathophysiology of IBS is complex and likely due to a combination of factors including altered motility, visceral hypersensitivity, dysbiosis, altered mucosal and immune function and central nervous system processing. The complex interplay between genetic, cultural, environmental and psychosocial factors, also known as the biopsychosocial model of disease, can lead to the development of functional GI disorders like IBS (Figure 1).iii

Treatment of IBS is multifaceted and ranges from exercise, dietary restriction, laxative or anti-diarrheal therapy, antispasmodics, Rifaximin, probiotics, and antidepressants. Psychological treatments to target the gut-brain axis such as cognitive-behavior therapy (CBT) have also been shown to be an effective therapy, and aims to address the psychological and environmental stressors that contribute to symptoms.iv,v,vi,vii,viii

This study will investigate the effectiveness of Zemedy, a mobile application that enables the digital delivery of a CBT program to people with IBS. CBT has been shown to reduce the severity of intractable IBS symptoms by as much as 70%, but the provision of the therapy is limited by the availability of qualified therapists to patients in need. Rooted in scientific evidence, Zemedy integrates the 8-week CBT program with other in-app features – such as educational modules and health trackers, to provide an end-to-end IBS management tool. The delivery of the CBT program in itself is guided by a chatbot persona, Elle, that mimics the conversation lead by a healthcare professional in a clinical therapy setting. Educational modules on the Zemedy app range from topics on IBS causes and symptoms, to topics on relevant exercise and diet regimens. Health trackers on the Zemedy app can be used to record flare-ups, mood, and lifestyle information, allowing data to drive the extraction of meaningful patterns in IBS symptom presentation. Therefore, the Zemedy app grants IBS patients the option of and access to invaluable treatment streams.

## Biopsychosocial Conceptual Model

[figure not shown]

**Figure 1.** A biopsychosocial conceptualization of the pathogenesis, clinical experience, and effects of functional GI disorders. There is a relationship between early life factors that can influence the psychosocial milieu of the individual, their physiological functioning, as well as their mutual interaction (brain-gut axis). These factors influence the clinical presentation of the disorder and the clinical outcome. Modified from Rome III.

## Study Overview

This is an interventional, randomized controlled study with two study arms. The study will utilize Zemedy which provides digital delivery of a CBT program to people with IBS, via a smartphone application.

The study will involve a minimum of 44 individuals (randomized 22 in study group and 22 in the control group) with irritable bowel syndrome, who will take part in the intervention for 8 weeks. The study group will receive treatment as usual (TAU) + Zemedy intervention and the control group will receive TAU. TAU for IBS is tailored to the patient and may involve dietary modification, exercise, antispasmodic medication, laxative therapy, anti-diarrheal therapy, and pain medication. Patients will be evaluated in clinic or via telehealth at the beginning of the study, and at weeks 8 and 24. Patients can contact the physician electronically via the MyHealth application in between visits.

**Figure 2: Overview of study design**

## Study objectives

- Determine the efficacy of the Zemedy application in the reduction of irritable bowel syndrome symptoms

## **Study design**

- Single-blind randomized controlled trial
- Duration: 24 weeks, intervention is 8 weeks long

## **Primary Endpoint**

- Change in IBS symptoms based on the IBS symptom severity score (SSS) score at week 8 compared to baseline

## **Secondary Endpoints**

- Change in IBS symptoms based on the IBS-SSS- at week 24 compared to baseline
- Cohen Perceived Stress Questionnaire (PSQ)
  - Measures degree situation's in one's life are seen as stressful
  - Survey will be distributed at weeks 0 and 24 of the study
- Work and social adjustment scale (WSAS)
  - Measures the effect of IBS on ability to work and manage at home, participate in social and private leisure activities and maintain relationships.
  - Survey will be distributed at weeks 0 and 24 of the study
- Subject's Global Assessment of Relief (SGA)
  - Assesses global symptoms relief asking the question, "Overall, how do you feel?". Scale of -2 to +2 , from completely worse to completely better. 1–2 considered responders and 4–5 non-responders.
  - Survey will be distributed at weeks 0 and 24 of the study
- Hospital Anxiety and Depression Scale (HADS).
  - Assesses mood measured by the total distress score (<7 normal, 8-14 borderline, 15 or >15, abnormal)
  - Survey will be distributed at weeks 0, 8 and 24 of the study
- Work Productivity and activity impairment (WPAI) questionnaire
  - Assesses work productivity based on number of days taken off from work due to health
  - Survey will be distributed at weeks 0, 8 and 24 of the study
- Fecal Sampling and Microbiome analysis (optional; opt-in)
  - Assessment of any changes in gut flora (baseline vs after intervention)
  - Stool self collection will occur at weeks 0 and 8 of the study. An additional collection may occur at week 24, contingent on PI judgment.
- Adherence to intervention assessed by use of Zemedy application in the Zemedy arm
- Decreased urgent care/ER/physician appointments due to the patient's IBS
- Application is considered to be safe without adverse events such as worsening irritable bowel syndrome symptoms, hospitalizations, worsened or new mood changes

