### Outcome assessment

- Assess outcomes at weeks 8 and 24, after randomization by randomization software

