#### Statistical evaluation

The statistical analyses will be done in cooperation with a statistician. The analyses will compare scores in each evaluation point between evaluation points between the intervention and the control group. Outcomes will be assessed at weeks 8 and 24 of the study. Analyses will be conducted on the full sample (intent to treat analysis).

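### The SGA responder codes do not fit the stated SGA scale; as a lesser point, PSQ, WSAS and SGA have no week-8 reading

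*Combined protocol and SAP*

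**What the plan says.** **SGA coding.** Secondary Endpoints describes the SGA as a global relief item that asks how the patient feels overall. The scale is given as "Scale of -2 to +2 , from completely worse to completely better" and the classification as "1–2 considered responders and 4–5 non-responders". No other section restates or repairs the coding. Statistical evaluation speaks only of comparing scores between the arms and does not mention responder rates.

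**Timing.** Under each of PSQ, WSAS and SGA, the same section says "Survey will be distributed at weeks 0 and 24 of the study". Table 1 and the Schedule of Assessments show the same pattern. HADS and WPAI are collected at weeks 0, 8 and 24, and IBS-SSS at weeks 0, 4, 8 and 24. Study design gives "Duration: 24 weeks, intervention is 8 weeks long", and the primary endpoint is "Change in IBS symptoms based on the IBS symptom severity score (SSS) score at week 8 compared to baseline". For the optional stool samples, collected at weeks 0 and 8 with a possible further one at week 24, the stated purpose is "Assessment of any changes in gut flora (baseline vs after intervention". Two general statements name both time points without exception: "Assess outcomes at weeks 8 and 24, after randomization by randomization software" (Outcome assessment) and "Outcomes will be assessed at weeks 8 and 24 of the study" (Statistical evaluation).

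**The concern.** A responder definition is a decision threshold. If its codes are not on the scale, whoever analyses the data has to choose a rule, possibly after seeing the answers. The choice is not cosmetic: depending on how the codes are read, a patient who reports being completely better counts as a responder or as a non-responder.

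On timing, three of the five secondary questionnaires have no value at the end of the intervention. If PSQ, WSAS or SGA shows no difference at week 24, the data on that instrument cannot tell an effect that never occurred from one that was present at week 8 and faded. The week-8 primary result also has no patient-rated global relief score beside it. A missed week-8 reading cannot be collected later.

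**Working it through.** The plan states no figure for the SGA, PSQ or WSAS, so there is none to reproduce. The check sets the codes against the scale, then counts readings and days.

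**1. SGA codes against the scale.** Assume whole-number answers, so the stated scale has five values. Apply the stated rule (1 or 2 = responder, 4 or 5 = non-responder) under three readings:

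| Answer on the stated scale | Codes as stated, -2 to +2 | Recoded 1 to 5 in the stated order (worse to better) | Recoded 1 to 5 in reverse order (better to worse) |
|---|---|---|---|
| -2 | unclassified | 1: responder | 5: non-responder |
| -1 | unclassified | 2: responder | 4: non-responder |
| 0 | unclassified | 3: unclassified | 3: unclassified |
| +1 | responder | 4: non-responder | 2: responder |
| +2 | responder | 5: non-responder | 1: responder |

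- As stated: {4, 5} shares no value with {-2, -1, 0, 1, 2}. There are no possible non-responders, and 3 of 5 values are unclassified.
- On 1 to 5, in either direction: 1 of 5 values is unclassified (3).
- On 1 to 5 in the stated order, responders are the two worse answers, the opposite of the first reading.
- Only the reverse order gives both groups a sensible meaning. It runs against the direction the plan states and still leaves 3 unassigned.

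No reading classifies every answer.

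**2. Readings at week 8.** From Table 1 and the Schedule of Assessments, outcome questionnaires at week 8 are IBS-SSS, HADS and WPAI: 3 of 6. Of the five secondary questionnaires other than IBS-SSS, PSQ, WSAS and SGA (3 of 5) have none.

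**3. Distance from the end of the intervention.** The only post-baseline reading of these three is on Day 168.
- Nominal: 168 - 56 = 112 days = 16 weeks.
- Visit to visit, with the ±3-day window at both ends: 165 - 59 = 106 days to 171 - 53 = 118 days.

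**4. Effect of adding week-8 readings.** Count one between-arm comparison per questionnaire at weeks 8 and 24, leaving out the primary.
- Now: IBS-SSS week 24 (1) + PSQ (1) + WSAS (1) + SGA (1) + HADS (2) + WPAI (2) = 8.
- With SGA at week 8: 9. With all three: 11.
- As illustration only, if each were tested at 0.05 and all were independent (the plan states neither), the chance of at least one false positive would be 1 - 0.95^8 = 0.34 now, 1 - 0.95^9 = 0.37 with SGA, and 1 - 0.95^11 = 0.43 with all three.
- Outcome questionnaires at week 8 rise from 3 to at most 6, the number already asked at weeks 0 and 24. Counting the medication form, week 8 rises from 4 forms to at most 7, against 6 at week 24.

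**The case against.** **On the coding.** A reader might infer that the SGA cannot be analysed at all. The documents do not support that. Statistical evaluation plans to compare scores, and a score from -2 to +2 can be compared between arms as it stands. On that scale +1 and +2 are even identifiable as responders, so a proportion could be computed if everyone else were counted as a non-responder. That last step is an assumption the plan does not make, and it replaces the codes the plan does give. The mismatch therefore stands, limited to the responder classification. The reversal of direction depends on a 1-to-5 coding that the documents never state.

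**On the timing.** Most of the opposing case stands. Three places agree on the schedule. Amendment 2 records that scheduling typos in this section were corrected and HADS was added at week 8, and the current text still has these three at weeks 0 and 24, so the choice may be deliberate. Reading some secondary instruments only at the last visit is a legitimate way to look at durability. Fading can be examined on IBS-SSS, HADS and WPAI. The sample size is justified for IBS-SSS only, so a week-8 reading would resolve only part of the ambiguity of a null result: two null results could also reflect low power.

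Three stronger readings are tempting and go too far:
- *The schedule contradicts Outcome assessment and Statistical evaluation.* Those sentences can be read as a general summary of the assessment times.
- *Week 24 is the only informative SGA reading.* The worse-to-better anchors suggest it, but the item as given does not refer to the time since treatment began. Patients enter on a stable regimen, so a week-0 answer could describe their state on usual care.
- *The primary endpoint is weakened.* It is a separate instrument, collected at week 8 as planned.

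**Conclusion.** The SGA responder definition is wrong as written. On the stated scale it yields no non-responders and leaves 3 of 5 values unclassified; on a 1-to-5 coding it leaves 1 of 5 unclassified and, in the stated order, labels the worse end as responders. This rests only on the wording of Secondary Endpoints and on whole-number answers. It affects one secondary endpoint's classification, not the comparison of raw SGA scores.

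The missing week-8 reading of PSQ, WSAS and SGA is a gap for which no reason is given, and closing it would be a low-cost improvement; it is not an error. The case is strongest for the SGA, because no other listed questionnaire asks for global relief, whereas HADS and WPAI give related, though not equivalent, week-8 information beside PSQ and WSAS. That ranking is a judgement. The randomised week-24 comparison remains valid for all three instruments.

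**What to change.** **Correct the SGA definition (needed whatever is decided on timing).** In Secondary Endpoints, state one numeric scale, say which end is better, and assign every code, including the middle one, to responder or non-responder before the data are analysed. One wording that keeps the stated scale and the stated responder codes would make +1 and +2 responders and -2, -1 and 0 non-responders. The sponsor should check it against the answer form actually used and decide deliberately where 0 belongs. The cost is a few words.

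**Consider a week-8 reading.** Add the SGA first, and PSQ and WSAS if burden allows, to the week-8 column of Table 1 and of the Schedule of Assessments, and change the matching lines in Secondary Endpoints to weeks 0, 8 and 24. Label the new comparisons supportive. No new visit is needed. The costs are:
- one to three more questionnaires at week 8;
- secondary questionnaire comparisons rising from 8 to between 9 and 11, in a plan with no stated multiplicity rule;
- an amendment that needs IRB review;
- no week-8 value for patients already past that visit. The documents do not give enrolment status, so the size of this loss is unknown.

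**If the schedule is kept,** add a clause to Outcome assessment and to Statistical evaluation saying that PSQ, WSAS and SGA are assessed after baseline at week 24 only, and give the reason.

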### Power

We estimate that with an initial sample size of 22 participants per intervention group and 22 per control group, we will have 80% power (alpha 0.05) to detect the minimal clinically important difference on the IBS-SSS. We expect a minimum reduction in score

of 50 points, which is considered to be a considerable improvement.ix In order to account for patient withdrawal from the trial we aim to enroll 30 patients in each study group.

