### Amendment 2 (Protocol Version 3)

- Correction of scheduling typos in secondary endpoint section
- Addition of HADS assessment to Week 8 visit in the schedule of assessments
- Adjustment to HADS abnormal threshold ( >15 instead of >11)
- Adjustment to exclusion criteria
  - Removal of
    - Severe anxiety or depression assessed by the HADS scale
  - Addition of
    - Psychiatric hospitalization within 10 years
    - Active (within the past 3 months) suicidal ideation
- Addition of safety assessment for suicidal ideation to Physician's Visit
- Addition of gastroenterology psychologist consult
  - for adverse events
  - for interim safety analysis

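### The SGA non-responder codes (4–5) lie off the stated −2 to +2 scale, so no answer can be a non-responder and −2, −1 and 0 have no class (secondary endpoint only)

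*Combined protocol and SAP*

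**What the plan says.** The SGA is listed under Secondary Endpoints as a single question on overall symptom relief. Its range and direction are given as "Scale of -2 to +2 , from completely worse to completely better". The sentence that follows sets the response rule: "1–2 considered responders and 4–5 non-responders". On timing, the same entry says "Survey will be distributed at weeks 0 and 24 of the study", and both Table 1 and the Schedule of Assessments agree.

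Statistical evaluation does not mention SGA scoring. Its general statements are "The analyses will compare scores in each evaluation point between evaluation points between the intervention and the control group" and "Analyses will be conducted on the full sample (intent to treat analysis".

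The Amendment Summary records "Correction of scheduling typos in secondary endpoint section" for protocol version 3, which concerns timing. It lists no change to SGA scoring.

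**The concern.** Two adjacent sentences in the current text cannot both apply. One fixes the possible answers; the other assigns the non-responder label to values outside them. The responder half works on the stated scale, since +1 and +2 are the two better-than-neutral answers. The non-responder half matches no possible answer, and the neutral and worse answers are left without a class.

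The SGA is collected only at weeks 0 and 24, so each patient has one post-baseline answer to classify. If that answer is neutral or worse, the written rule gives no result. Someone then has to decide, possibly with the data in view, whether such patients count as non-responders, form a separate class or drop out of the denominator. That choice moves the responder rate, so it should be made beforehand.

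**Working it through.** There is no stated figure to reproduce: the sample size and power statement concern the IBS-SSS and do not use the SGA. The check is an enumeration.

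**Inputs**, all from the SGA entry under Secondary Endpoints:
- Range −2 to +2, with low meaning worse and high meaning better.
- Responder codes {1, 2}; non-responder codes {4, 5}.
- Assumption: answers are whole numbers, so the possible answers are −2, −1, 0, +1, +2.

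**Step 1: apply the written rule to the stated scale, then test a 1–5 origin.** The 1–5 columns are inference, because no section mentions such a coding. R = responder, N = non-responder, U = unclassified.

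| Answer | Stated scale | 1–5, best = 1 (code = 3 − answer) | 1–5, worst = 1 (code = answer + 3) | One possible complete rule |
|---|---|---|---|---|
| −2 | U | 5: N | 1: R | N |
| −1 | U | 4: N | 2: R | N |
| 0 | U | 3: U | 3: U | N |
| +1 | R | 2: R | 4: N | R |
| +2 | R | 1: R | 5: N | R |
| Total | 2 R, 0 N, 3 U | 2 R, 2 N, 1 U | 2 R, 2 N, 1 U | 2 R, 3 N, 0 U |

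On the stated scale 3 of 5 answers have no class. With 1 as the best answer, a 1–5 coding gives sensible labels to four answers but leaves the neutral one unclassified. With 1 as the worst answer, it calls the worst answers responders, so that reading can hardly be intended. It shows only why the direction on the form needs confirming.

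**Step 2: what the literal rule does to a responder rate.** Let r be the number of responders in an arm. If only classified answers are counted, the rate is r/(r + 0) = 100% in any arm with at least one responder, whatever the treatment does. The literal rule therefore cannot yield a usable rate on that denominator.

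**Step 3: how much the class of the neutral answer matters.** Let n be the answered SGAs in an arm and n0 the neutral ones. Counting neutral as non-response gives r/n; leaving neutral answers out gives r/(n − n0). The ratio is

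[r/n] ÷ [r/(n − n0)] = (n − n0)/n = 1 − n0/n.

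The documents give no neutral share. For assumed shares of 10%, 20% and 40% the ratio is 0.90, 0.80 and 0.60. The comparator here excludes only neutral answers, as the 1–5 reading with 1 as best would do; it is not the rule as printed.

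**Step 4: look for a repair elsewhere.** Table 1 and the Schedule of Assessments give timing only. Statistical evaluation says that scores are compared and that the full sample is analysed, without defining SGA classes. The Amendment Summary describes no change to SGA coding. Nothing reconciles the two sentences.

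**The case against.** The best case against is that this is a coding slip in one of about ten secondary items, with an obvious reading: anyone not at +1 or +2 is a non-responder. Statistical evaluation plans a comparison of scores and names no SGA responder analysis, so the main comparison could go ahead untouched. On that view, the only real ambiguity is the class of 0.

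Much of this stands. Raw scores remain comparable, and the practical question is mainly how to treat the neutral answer. It is also right that the full-sample statement says who is analysed, not which class a neutral answer belongs to. It argues against dropping those patients, but a three-class analysis (better, same, worse) would also keep them. If the codes did come from a 1–5 scale, the gap at 3 might even be deliberate, so treating 0 as non-response is a choice to be made and not a restoration of known intent.

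What does not stand is the suggestion that the text can be left alone. The protocol does not define non-responders as everyone else; it names a separate set of codes, and that set is impossible on the stated scale. A reader cannot settle the neutral class from the documents.

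**Conclusion.** The concern holds. As written, with whole-number answers, the SGA rule yields 2 responder answers, 0 non-responder answers and 3 unclassified answers out of 5. It is an error in a current endpoint definition and should be fixed before the SGA is scored.

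Its reach is limited to any SGA responder result. It does not affect the IBS-SSS primary endpoint, the sample size or a comparison of raw SGA scores, and no effect on a treatment difference is claimed. The finding does not depend on the 1–5 explanation, which remains an inference, or on the assumed neutral shares, which only illustrate sensitivity.

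**What to change.** State one scale and one direction, and give every possible answer exactly one class. One possible wording: SGA responder at week 24 = +1 or +2; non-responder = 0, −1 or −2. If the sponsor prefers a separate neutral class, say so and state how it enters the analysis. Confirm that the data-capture form uses the same codes and direction.

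This wording classifies only answers that were given. The denominator and the handling of a missing week 24 SGA need their own sentence, because the Power section expects dropout: "In order to account for patient withdrawal from the trial we aim to enroll 30 patients in each study group". Against the 22 per arm used for power, that is a margin of 30 − 22 = 8 per arm (8/30 = 26.7%); the subtraction is mine, and the protocol sets no limit on withdrawal.

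The cost is one line of text and a check of the form codes. The downside of counting neutral as non-response is a lower responder rate in both arms than if neutral answers were left out, by the factor 1 − n0/n shown above.

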## Patient visits

- Patients will be seen in clinic at weeks 0, 8 and 24. Patients will be seen either in person or via telehealth. Consent will be obtained at the initial clinic visit either online via Recap or by paper. Optional microbiome analysis samples will be self-collected by patients at weeks 0 and 8 (and possibly 24) and returned by mail or in person. Stool collection kits will be given or mailed after consent, and CBT patients instructed to begin use of the app only after the first stool collection. The physician assessment will include a safety assessment for suicidal ideation.

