#### Ethical considerations

Completing the questionnaires, taking part in the digital program, being in the control group, and all other time spent related to the study are additional efforts to the treatment the subjects would otherwise receive. In our view, the burden of taking part in the study is moderate for the participant. They are advised to contact the study PIs at any point if any questions or adverse effects arise. An interim safety analysis will be performed under consultation with the team gastroenterology psychologist.

All participating individuals will sign an informed consent to take part in the study and they will have an appropriate amount of time to familiarize themselves with the study before making the decision to participate. The study and all related activities such as extra phone consultation are completely free of charge for the participants. The results are confidential and will be kept in a safe and encrypted storage within the Redcap system (more information in the Data collection chapter). The statistical analyses will be performed without any personal identification information by assigning anonymous identification codes to all subjects.

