#### Adverse experience reporting

Any adverse experiences with the Zemedy Program will be monitored during the study by the study investigators. PIs will consult with the team's Gastroenterology psychologist.

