#### Study completion

Patients who have completed all of the IBS-SSS at weeks 0, 4, 8, and 24 will be considered completers of the study.

SCHEDULE OF ASSESSMENTS				
Protocol Activity	Week 0 Day 0*	Week 4 Day 28*	Week 8 Day 56*	Week 24 Day 168*
Informed consent	X			
Inclusion/Exclusion Screening	X			
Randomization	X			
Zemedy onboarding (if CBT)	X			
Physician Visit	X		X	X
Demographic Information	X			
Current Medications	X	X	X	
Fecal Sampling/Microbiome (opt-in)	X		X	X**
IBS-SSS	X	X	X	X
PSQ	X			X
WSAS	X			X
SGA	X			X
HADS	X		X	X
WPAI	X		X	X
Compensation			X	X

\*The study window is six days, + / - 3 days from the noted day.

\*\*Sample collection contingent on PI judgment.

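### The safety endpoint has no control-arm comparator, so harm from the app cannot be separated from the natural course of IBS and mood

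*Combined protocol and SAP*

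**What the plan says.** All references are to the combined protocol and SAP.

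- **Secondary Endpoints**, last bullet: "Application is considered to be safe without adverse events such as worsening irritable bowel syndrome symptoms, hospitalizations, worsened or new mood changes". No amount of worsening, time window or comparison group is given.
- **Adverse experience reporting**: "Any adverse experiences with the Zemedy Program will be monitored during the study by the study investigators". It adds "PIs will consult with the team's Gastroenterology psychologist", without relatedness categories.
- **Statistical evaluation**: "The analyses will compare scores in each evaluation point between evaluation points between the intervention and the control group". Analyses are on the full sample by intention to treat, with outcomes at weeks 8 and 24. Events are not mentioned.
- **Ethical considerations**: "An interim safety analysis will be performed under consultation with the team gastroenterology psychologist", with no stated content. Of participants it says "They are advised to contact the study PIs at any point if any questions or adverse effects arise".
- **Patient visits**: "The physician assessment will include a safety assessment for suicidal ideation". The Schedule of Assessments puts physician visits at weeks 0, 8 and 24 for all participants.
- **Table 1 and the Schedule of Assessments**: IBS-SSS at weeks 0, 4, 8 and 24 and HADS at weeks 0, 8 and 24, without restriction by arm. Neither has a row for adverse events or hospitalisations, and the Data collection section lists neither.

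**The concern.** IBS symptoms and mood rise and fall without any app. A statement about events in the app arm alone therefore has no reference level. If every event counts, a harmless app will collect some. If only events attributed to the app count, the result rests on a judgement with no stated rule and no control counterpart, because a TAU patient cannot have an adverse experience with an app that he or she does not use.

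The planned score comparison helps only in part. Mean IBS-SSS or HADS can improve while a minority of patients deteriorate, and a hospitalisation has no score. At stake is the safety conclusion of the trial. The primary endpoint is not affected.

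**Working it through.** **1. What the plan uses from each arm.**

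| Element | App arm | TAU arm |
|---|---|---|
| IBS-SSS and HADS scores | collected, compared | collected, compared |
| Suicidal ideation at physician visit | assessed | assessed |
| Advice to report adverse effects | yes | yes |
| Adverse experience monitoring | worded for the app | not covered by the wording |
| Count of events or of patients who worsen | not planned | not planned |

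The raw material for a comparison is largely there. What is missing is event collection on the same footing in both arms, and the comparison itself.

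**2. What zero events would show.** The plan states no figure for safety, so there is none to reproduce. Inputs are n = 22 and n = 30 per arm, both from the Power section. With no events in n patients, the exact two-sided 95% upper limit solves (1 − p)^n = 0.025, so p = 1 − 0.025^(1/n).

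- n = 22: 1 − 0.025^(1/22) = 0.154
- n = 30: 1 − 0.025^(1/30) = 0.116

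This needs no assumed event rate.

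**3. Illustration of background events.** The documents give no background rate, so these rates are assumptions. P(at least one event with a harmless app) = 1 − (1 − p)^n:

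| Assumed p | n = 22 | n = 30 |
|---|---|---|
| 2% | 36% | 45% |
| 5% | 68% | 79% |
| 10% | 90% | 96% |

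These figures show that some events are to be expected. They are not the failure rate of a rule that the plan states.

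**4. What a by-arm comparison would deliver.** Newcombe interval: let d = p1 − p2, with Wilson limits (l1, u1) and (l2, u2). The lower limit is d − √[(p1 − l1)² + (u2 − p2)²] and the upper limit is d + √[(u1 − p1)² + (p2 − l2)²]. Enumerating all pairs of binomial outcomes exactly gives:

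| Quantity | 22 per arm | 30 per arm |
|---|---|---|
| Mean half-width, 10% v 10% | 19.9 points | 16.7 points |
| Mean half-width, 20% v 20% | 23.2 points | 20.0 points |
| 0 v 0 events | ±14.9 points | ±11.4 points |
| P(lower limit > 0), 30% v 10% | 38% | 49% |
| P(lower limit > 0), 40% v 20% | 30% | 39% |

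**5. Why the 20% row matters.** The Power section gives 22 per arm, 80% power, alpha 0.05 and 50 points, but no SD. Solving backwards, two-sided: SD = 50 / [√(2/22) × (1.960 + 0.842)] = 59.2, or 57.8 with a t test. Suppose that this SD applies to change scores, that changes are normal, and that the mean change is zero (all assumptions). Then the share of patients who rise by 50 points or more is P(Z > 50/59.2) = 20%, or P(Z > 50/57.8) = 19%. The plan uses 50 points for improvement only; here it serves to size the intervals.

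**The case against.** The strongest reply is that the bullet sets no pass/fail rule. The bullet just before it, on fewer health-care visits for IBS, is also phrased as a desired result, and no stopping decision hangs on either. This stands. A reader might infer that a single adverse event would make the plan declare the app unsafe, but the documents do not say so. The probabilities in step 3 are therefore illustrations only.

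A reader might also infer that TAU patients have no safety follow-up. The documents do not support that either: they have the same physician visits, the same suicidal-ideation assessment and the same advice to report problems.

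There is also other information from both arms. The Subject's Global Assessment has a worse end and is scheduled at week 24, and IBS-related urgent care, emergency and physician visits are an endpoint. These narrow the gap but do not close it. Neither is an adverse-event count, and the response categories given for the Global Assessment (1–2 and 4–5) do not fit its −2 to +2 scale.

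Finally, the missing worsening threshold, attribution rule and interim-analysis content could each be called detail to be filled in later. Taken singly, that is fair. The absent comparator is different: it is a feature of the method as written, and events not collected alike in both arms cannot be reliably recovered afterwards.

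**Conclusion.** The point holds as one about the missing comparator. Followed as written, the plan gives a safety conclusion that makes no use of TAU event data and cannot separate app harm from the natural course of IBS and mood. Even the most favourable result, no events, would be compatible with a true event rate of up to 15.4% (n = 22) or 11.6% (n = 30). Those limits rest on sample size alone and would apply to any trial this small, so better wording will not remove them.

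The change should be made while events can still be collected alike in both arms. The finding does not show that the app is unsafe, that safety oversight is absent, or that a zero-event rule is in force.

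**What to change.** **Wording.** Reword the safety bullet in Secondary Endpoints as a by-arm comparison. Reword Adverse experience reporting so that adverse events and hospitalisations are asked about with the same questions in both arms at the existing week 8 and 24 physician visits. Week 4 is a questionnaire contact without a physician visit, so use only its IBS-SSS score.

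**Analysis.** Report by arm, all-cause, with risk differences and 95% Newcombe intervals:

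1. patients with IBS-SSS worsening from baseline at weeks 4, 8 and 24, from scores already collected;
2. patients with HADS worsening from baseline at weeks 8 and 24;
3. patients with any hospitalisation by week 24.

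The investigators should fix the worsening thresholds for reporting before any unblinded analysis. Give the denominator and the number of missing scores by arm. Judged relatedness to the app can follow as a secondary table for the app arm. State which of these counts the interim safety analysis will use.

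**Cost.** Protocol wording and a few questions at visits already scheduled. The main limitation is precision: mean half-widths of about 20 / 17 points at a 10% rate and 23 / 20 points at a 20% rate, for 22 / 30 per arm. Even a true increase of 20 points would often go undetected (step 4), so the result should be presented as a descriptive estimate and not as proof of safety.
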